The objective of this study is to measure the structural changes that occur in the foot when wearing arch supports, and how these changes correlate with overall relief of common structural-related foot ailments; plantar fasciitis, metatarsalgia, and/or hallux valgus

Specific Aim #1:

Measure any changes that occur in the position and alignment of the foot bones relative to one another using weight bearing radiographs and weight bearing CT scans, with and without over-the-counter arch supports under the sole of the feet.

Hypothesis: Arch supports (orthoses) will alter the positioning and alignment of the bones of the foot when standing. Any changes will be measurable in three dimensions, using both weight bearing CT scans and standard anterior-posterior and lateral radiographs.

Specific Aim #2:

Demonstrate if there is a correlation between symptomatic relief of painful foot conditions including hallux valgus, pes planus, metatarsalgia, as well as low back, knee and ankle pain using validated clinical scores and quality of life measures.

Hypothesis: Painful foot conditions as well as certain types of low back, knee, and ankle pain will improve when subjects wear over-the-counter arch supports on a regular basis, as demonstrated by validated subjective scoring.

3. General Description of Study Design

This study is a single armed prospective case series designed to evaluate the efficacy of treating common structural-related foot ailments (i.e. plantar fasciitis, metatarsalgia, and/or hallux valgus) with a high quality non-custom made arch support. It is believed that these conditions are the result of inadequate or poorly fitted arch supports resulting in a lack of structural correction in the foot while weight bearing. Over-the-counter insoles are believed to counteract the shortcomings in foot structure that result in these painful conditions. In this study, it is proposed that changes in foot morphology can be measured quantitatively using weight bearing CT Scan (Computerized Tomography) and X-rays of the subject with and without the arch supports. Subjects will also answer questions from a validated series of questionnaires pertaining to their foot condition and generalized health and activity level.

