The study is a minimal risk study, with all subjects receiving the arch supports being investigated. There is no placebo offered. Initial evaluation of all subjects will include all imaging and measurements. Collection of subjective responses will occur after 4 weeks, 8 weeks, and 12 weeks of treatment.

4. Subject Selection

A total of 50 subjects will be enrolled. Subjects must meet the following inclusion and exclusion criteria:

Inclusion

1. Men or women ≥ 18 and ≤ 65 years of age

2. The subject is able and willing to comply with study procedures and a signed and dated informed consent is obtained
3. Subjects diagnosed with symptomatic hallux valgus and/or plantar fasciitis and/or metatarsalgia.
4. Patient has had foot pain for at least 30 days.
5. Willing and able to utilize insole when walking for 90 days.
6. BMI \leq 35
7. Able to walk up to 0.5 miles without difficulty, in a 24-hour period.

Exclusion

1. Inability or unwillingness to comply with study procedures
2. Gross asymmetry in feet, where shoe size differs by 2 or more full sizes between right and left foot
3. Subject has had a CT performed within the last 30 days, for any body part.
4. Prior partial or total amputation of a foot
5. BMI $<$ 35.
6. Unilateral or bilateral foot deformity that would hinder the fitting of an over-the-counter arch support, such as active Charcot foot or Charcot with boney prominence
7. Ulcers or open sores on either foot
8. Currently wearing custom shoes or insoles.
9. Currently ambulating with a cane, crutches, walker.
10. Currently using any type of foot or ankle brace, and/or having used a brace in the last 30 days.
11. Pregnancy

Subject Recruitment:

Subjects will be recruited from the clinicians in the Division of Podiatry under the Department of Orthopaedics. Additionally, the sponsor, Good Feet Worldwide has a trade store the MGH service area, and will allow us to promote the study at their location with an advertisement poster. Potential subjects from the trade store will be referred to our clinics for screening and, when appropriate, recruited for the study.

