6. STUDY PROCEDURES

Table 1: Schedule of Visit Activities

Study Procedures	Screening and Treatment	Follow-up Visits (Every 28±3 days)			
		Week 0	Week 4	Week 8	Week 12
		Visit 1	Visit 2	Visit 3	Visit 4
Informed Consent	X				
Inclusion/Exclusion Criteria	X				
Medical History and Demography	X				
Urine Pregnancy test for women	X				
Physical Exam (incl Ht & Wt)	X	X	X	X	
Selection and fitting of insoles	X				
Clinical assessment of Foot Function	X	X	X	X	
Weightbearing CT w & w/o insoles	X				
Weightbearing X-ray w & w/o insoles	X				
Administer VAS, OFS exam	X	X	X	X	
Review Diary		X	X	X	
Schedule subsequent visits	X	X	X		
Record Adverse Events		X	X	X	

a. Screening / Baseline – Visit 1 (Day 1)

Informed consent must be obtained from each subject before any study procedure can commence. The consent form will be given on an IPad via RedCap signed on paper. The subject will sign and date the Informed Consent Form and undergo the following evaluations/procedures:

Medical History and Physical Assessment

- Determination of eligibility based on inclusion/ exclusion criteria
 - Urine pregnancy test for all women. Pregnant women are not eligible to participate.
- Demographics (date of birth, gender, race) will be recorded
- Medical history: relevant medical history, including history of current disease, and information regarding underlying diseases will be recorded.
- Physical exam will be performed and results recorded
- Height and weight will be measured and recorded.
 - Calculate subject's Body Mass Index

Foot Assessment

- Clinical evaluation of feet will be performed by Podiatrist Study Investigator
 - Classification of foot type
 - Pathologies and painful conditions will be identified
 - Additional ancillary conditions will be included in the history
 - Back, Knee, and Ankle pain along with associated diagnoses and prior treatments
 - Dermatologic conditions
 - Neurovascular measurements
 - Assessment of standard shoe gear
 - Generalized foot appearance (i.e. edema, tender areas, etc.)
 - Basic gait assessment

Subjective Pre-Treatment Assessment:

- VAS (Visual Analog Scale) and OFS (Orthopedic Foot Score) data collected to determine pre-treatment levels of pain and function. The following validated questionnaires will be completed by each study subject.
 - ACFAS Universal foot Evaluation
 - AOFAS Outcome score
 - Oswestry Low Back Disability score
 - Pain Intensity Score
 - Global Health Test
 - Pain Interference

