- Pre-treatment assessment to be completed on day one.
- Subjects will describe their immediate impressions without and with the arch support in place.

Insole Selection

- Based on clinical assessment, properly sized set of arch supports and properly fitted athletic shoes will be dispensed to the study subject. Fit and comfort will be confirmed before proceeding with other data collection steps.

Baseline Measurements

- Each subject will have one weight bearing CT and one weight bearing X-ray series (AP/Lateral) taken barefooted and a second series taken with the selected arch support in place. Subjects are enrolled sequentially, and there is no placebo group.
- Image analysis will compare position and alignment of bones of the foot to measure differences in positioning with and without arch supports, using CT and X-ray. X-ray measurements will include intermetatarsal angles, hallux abductus angle, sesamoid position, metatarsal declination angle, calcaneal inclination angle, talocalcaneal angle, calcaneocuboid angle, and overall morphology. CT measurements will be used to determine the 3-dimensional positioning of the foot bones, and will document the change in position that occurs with and without arch support.

Logging of Activities and Symptoms

- Study subjects will be issued a diary and they are to record the following data on a weekly basis. The diary will be sent to the patient via email and RedCap links.
 - Estimated distance walked (Those able to count steps are encouraged to do so.).
 - Activities of Daily Living
 - Symptoms, and level of pain rated on a VAS scale.
 - Compliance with wearing of insoles and athletic shoes

b. Treatment Phase

We will be conducting follow up surveys via email and RedCap links with patients.

Monthly follow up (End of weeks 4, 8, and 12)

- Confirmation of eligibility based on inclusion/ exclusion criteria
- Medical history: New or relevant changes to medical history, including history of current disease, and information regarding underlying diseases will be recorded
- Review of logged data from daily diary
- Completion of physician re-assessment and OAS and VAS scoring.
- Validated questionnaires will be completed at each of the 3 follow-up visits.
 - ACFAS Universal foot Evaluation
 - AOFAS Outcome score
 - Oswestry Low Back Disability score
 - Pain Intensity Score
 - Global Health Test
 - Pain Interference
- Record any Adverse Events

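### Part of Aim 2 cannot be answered as planned: knee and ankle pain have no named follow-up score, and the default analysis of the back score dilutes any effect

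*Combined protocol and SAP*

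**What the plan says.** **Aim and hypothesis (Section 2).** Aim 2 concerns "painful foot conditions including hallux valgus, pes planus, metatarsalgia, as well as low back, knee and ankle pain". Its hypothesis is that "Painful foot conditions as well as certain types of low back, knee, and ankle pain will improve when subjects wear over-the-counter arch supports" regularly, "as demonstrated by validated subjective scoring". The overall objective in the same section is narrower: "overall relief of common structural-related foot ailments; plantar fasciitis, metatarsalgia, and/or hallux valgus".

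**Entry (Section 4).** Inclusion 3 reads "Subjects diagnosed with symptomatic hallux valgus and/or plantar fasciitis and/or metatarsalgia", and inclusion 4 reads "Patient has had foot pain for at least 30 days". No back, knee or ankle pain is required.

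**Prescreen script (Section 5).** The script adds low back pain that worsens with walking to the conditions that let a caller continue. It later describes the study as covering knee, hip and low back pain too.

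**Measurement (Section 6).** Each subject completes six questionnaires at baseline and at each of the three follow-up visits: two foot scores (ACFAS, AOFAS), the "Oswestry Low Back Disability score", and three general ones (Pain Intensity, Global Health, Pain Interference). A VAS is given at all four visits and another is kept in the diary, neither with a stated body site. The baseline foot assessment takes a history of "Back, Knee, and Ankle pain along with associated diagnoses and prior treatments". Follow-up visits note changes in medical history.

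**Analysis (Section 9).** The plan is a repeated measures ANOVA, with Cohen's d for each variable: 0.20–0.49 small, 0.50–0.79 moderate, 0.80 and above large. No analysis set or subgroup is stated.

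**The concern.** The hypothesis sets its own standard of evidence, validated scoring, for pain at three sites outside the foot. For the knee and ankle, nothing listed meets that standard by name. A general pain score may fall over 12 weeks, but it cannot say which site improved.

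The back has a score, but not a population. Subjects are recruited for foot pain, and those without back pain have nothing to improve on Oswestry. If they are averaged in, the reported effect shrinks with their share, and the Section 9 bands could label a large effect small.

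Symptom change on these questionnaires is the primary endpoint. Knee and ankle scores that were not collected cannot be recovered later, and a back-pain subset chosen after seeing the data would carry little weight.

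**Working it through.** **Step 1. Match each site in the hypothesis to entry and outcome.**

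| Site | Required at entry? | Named follow-up score |
|---|---|---|
| Foot | Yes (inclusion 3 and 4) | ACFAS, AOFAS |
| Low back | No | Oswestry, all subjects |
| Knee | No | None; medical history only |
| Ankle | No | None named; medical history only |

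**Step 2. Match the condition lists.** Pes planus is in Aim 2 but not in inclusion 3. Plantar fasciitis is in inclusion 3 and the objective but not in Aim 2's list. Low back pain is in the prescreen script but not in the inclusion criteria, so a caller with back pain alone passes that question and then fails inclusion 3.

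**Step 3. Size of the dilution.** The sample size of 50 has no supporting power, effect size or SD, so there is no planned figure to reproduce. What follows is an illustration.

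From the documents: n = 50; alpha 0.05 (sidedness not stated, two-sided taken); the Cohen's d bands. Assumed:
- p, the share of subjects with back pain;
- d, the standardised change in those subjects (SD of change set to 1);
- mean change 0 with SD s = 0.2 to 0.5 in the rest;
- no dropout;
- a paired t test on change from baseline, power from the noncentral t.

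Formulas:
- mean change over all subjects = p·d
- variance = p(1 + d²) + (1 − p)s² − (p·d)²
- d over all subjects = p·d / √variance

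Worked case, p = 0.4, d = 0.80, mean 0.32:
- s = 0.2: variance = 0.656 + 0.024 − 0.1024 = 0.5776, SD 0.760, d = 0.32/0.760 = 0.42
- s = 0.5: variance = 0.656 + 0.150 − 0.1024 = 0.7036, SD 0.839, d = 0.32/0.839 = 0.38

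| d in affected | p | d over all 50 | Power, all 50 | Affected only (n) | Power, affected only |
|---|---|---|---|---|---|
| 0.80 | 0.3 | 0.31–0.35 | 57–69% | 15 | 82% |
| 0.80 | 0.4 | 0.38–0.42 | 75–83% | 20 | 92% |
| 0.80 | 0.5 | 0.45–0.49 | 88–92% | 25 | 97% |
| 0.80 | 0.6 | 0.52–0.55 | 95–97% | 30 | 99% |
| 0.50 | 0.4 | 0.26–0.29 | 43–51% | 20 | 56% |

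**Step 4. Sensitivity to s.** With p = 0.4 and d = 0.80, s = 0 (no change at all in unaffected subjects) gives d = 0.43 and power 85%. With s = 1 (the same SD of change as affected subjects), d = 0.30 and power 54%.

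**The case against.** A reader might infer that Aim 2 as a whole cannot be answered. The documents do not support that. The hypothesis opens with painful foot conditions, two foot scores cover these at every visit, and the overall objective names only foot ailments.

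Nor is plantar fasciitis left out of the study. Aim 2's list is introduced as non-exhaustive, and the objective, Section 3, inclusion 3 and the prescreen script all name the condition. Its absence from the list is a drafting mismatch. Pes planus is not an entry diagnosis, but nothing excludes it and foot type is classified at baseline; what is missing is an analysis by foot type.

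Follow-up is not silent on the knee and ankle: changes in medical history are noted and the diary records symptoms. Neither is a validated site score. The questionnaires' contents are not in the documents, so a foot score may hold ankle items; the point rests on what is named.

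That Oswestry will be averaged over everyone is an inference from universal completion and the lack of any stated subset. It is the default reading, not an explicit instruction.

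The prevalence of back pain is unknown, and the prescreen script's mention of it could raise the share. At 60% the loss of power is small and the label would be moderate.

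Finally, restriction has a cost. Choosing subjects by baseline pain, with no control group, invites regression to the mean, so the restricted d may be inflated. This stands and limits how the restricted result may be read.

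**Conclusion.** The point holds for the parts of Aim 2 outside the foot. The knee and ankle claims have no named outcome that could test them; this follows from the text and needs no assumption. For the back, the analysis set is unspecified, and the default dilutes the mean change to p times its value in affected subjects.

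The size rests on assumed p, d and s. A true d of 0.80 falls to 0.31–0.35 at 30% prevalence and 0.52–0.55 at 60%. For s between 0.2 and 0.5, a large effect is reported as small only up to about 50% prevalence. The harm is more to the reported effect size than to power: at 40% prevalence power is 75–83% over all subjects against 92% restricted, and the gap nearly closes at 60%. With d = 0.50 at 40%, restriction reaches only 56%, so it does not rescue a moderate effect. The foot part of the aim is unaffected.

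**What to change.** 1. **Back.** Prespecify, as a secondary analysis, the change in Oswestry in subjects whose Visit 1 history records back pain, reported beside the all-subjects result. Define the subset by the recorded history, not by the Oswestry score, to limit regression to the mean. State both downsides: fewer subjects, and a remaining regression effect that a single-arm design cannot separate from treatment effect.
2. **Knee and ankle.** Add a site-specific pain VAS line for each at all four visits, analysed as secondary in subjects with that pain at Visit 1. Otherwise delete knee and ankle from Aim 2 and its hypothesis.
3. **Condition lists.** Reconcile Aim 2 (pes planus, and plantar fasciitis for tidiness), inclusion 3 and the prescreen script (low back, knee, hip).

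The cost is wording in Sections 2, 5 and 9 and at most two extra VAS lines per visit. No visit is added, and the baseline history already identifies the subsets.

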o Thank you for your interest. You do not qualify to participate in this study but if you like, you may leave your name with us to participate in future studies.

• Yes

Before I describe the rest of the study to you, I have a few more questions to determine if you qualify.

Are you between the ages of 18 and 65 years old? Do you weigh less than 300 lbs.?

• No

o Thank you for your interest. You do not qualify to participate in this study but if you like, you may leave your name with us to participate in future studies.

• Yes

Mass General Brigham Institutional Review Board
Intervention/Interaction Detailed Protocol

Have you had surgery to your feet previously (not including toenail procedures)? Have you ever had any part of either foot amputated?

· Yes

o Thank you for your interest. You do not qualify to participate in this study but if you like, you may leave your name with us to participate in future studies.

· No

Is the difference in shoe size between your two feet 2 or more full sizes?

· Yes

o Thank you for your interest. You do not qualify to participate in this study but if you like, you may leave your name with us to participate in future studies.

· No

Do you currently wear custom-molded orthotics, or have you worn them in the last 30 days?

· Yes

o Thank you for your interest. You do not qualify to participate in this study but if you like, you may leave your name with us to participate in future studies.

· No

Have you ever been diagnosed with Neuropathy?

· Yes

o Thank you for your interest. You do not qualify to participate in this study but if you like, you may leave your name with us to participate in future studies.

· No

Allow me to tell you a little more about this study. We will be looking at the effect of arch supports on a variety of conditions, including bunions, metatarsalgia, plantar fasciitis, knee, hip, and/or lower back pain. We want to determine if wearing arch supports might help to relieve pain associated with these conditions.

In order to participate, you will be asked to go to come into the Good Feet store to be fitted for the arch support kit and for a new pair of shoes. You will then be referred to the Foot and Ankle clinic at Massachusetts General Hospital in Waltham, where you will receive the shoes and arch supports and be enrolled into the study.

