- Clinical photographs will be taken with and without the arch support in place, while barefooted.

c. Study Completion/Termination

When the subject completes the study, voluntarily withdraws, is withdrawn for any reason, the study is terminated, or the Investigator is no longer able to locate the subject, the reason for the withdrawal will be reported along with any relevant information concerning the device, subject condition or death.

All subjects withdrawn from the study due to an adverse event, or have an adverse device effect or serious adverse event at study completion, will be followed until the adverse device effect or serious adverse event is resolved, a resolution is no longer expected or it returns to baseline.

Treatment Discontinuation

After completing the estimated 12-week visit requirements, the subject will be considered to have completed the study. In all cases of withdrawal, the date and the reason for withdrawal are to be documented.

Primary Endpoint

The primary endpoint is the change in symptoms when arch supports are worn, as compared to baseline. Change in symptoms and relief of pain will be quantified based on subjective completion of validated questionnaires. Data from the questionnaires will provide a reliable assessment of symptomatic relief from the foot ailments being evaluated.

Secondary Endpoint

The secondary endpoint is the change in foot morphology when shoe inserts are worn. The change to be documented is the acute change that occurs in the boney structure of the foot when it is supported with the orthosis. A critical part of the analysis is to demonstrate if there are measurable changes in foot morphology when supported, and to determine if those changes correlate with symptomatic changes in the study subject's foot condition.

Remuneration

Study subjects will not be paid to participate in this study. However, all participants will receive new orthoses and new shoes, and will be permitted to keep these items at the conclusion of the study. Also, all study participants will receive up to \$50 to reimburse them for any travel expenses related to the study. We would like to pay the participants by check on the date of their visit, if permitted to do so.

Sharing of Data and Confidentiality

All data will be kept within the confines of MGH. Since there are no other sites involved in the study, no outside investigators will have a need for access to the data.

7. Risks and Discomforts

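### Exclusion 8 and the telephone script do not clearly bar current users of non-custom arch supports, so some day-one baselines may already be supported

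*Combined protocol and SAP*

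**What the plan says.** **Device and design.** Section 3 states "This study is a single armed prospective case series" and describes the product as a "high quality non-custom made arch support".

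**Eligibility.** Exclusion 8 in Section 4 removes people "Currently wearing custom shoes or insoles". It has no look-back period. Exclusion 10, on braces, is wider: "Currently using any type of foot or ankle brace, and/or having used a brace in the last 30 days".

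**Telephone screen.** The script in Section 5 asks "Do you currently wear custom-molded orthotics, or have you worn them in the last 30 days". It has no question on over-the-counter supports.

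**Recruitment.** Section 4 names the podiatry clinicians first. It adds that the sponsor, which has a store in the area, "will allow us to promote the study at their location with an advertisement poster".

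**Baseline and endpoint.** Section 6 says "Pre-treatment assessment to be completed on day one", with no run-in. It then defines the endpoint: "The primary endpoint is the change in symptoms when arch supports are worn, as compared to baseline". Section 9 describes the analysis as a comparison between wearing and not wearing the insoles. For imaging, the reference condition in Section 6 is barefoot.

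**Footwear record.** The Visit 1 foot assessment includes the subject's usual footwear. Nothing links that record to eligibility or to the analysis.

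**The concern.** With no control group, the day-one score has to stand for the unsupported state if the 12-week change is to be read as the effect of wearing supports. The criteria do not clearly secure this. The one class of device they fail to name is the class under study.

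A subject who arrives already wearing a non-custom support gives a baseline that is not free of treatment. That subject's symptom change compares one support with another. New study shoes go to everyone, so they are a separate matter and not specific to these subjects.

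The planned correlation between structural and symptomatic change is also affected. For such a subject the structural change is barefoot against support, while the symptom change is old support against new. The imaging endpoint on its own is not affected, because its barefoot reference is taken on the same day.

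**Working it through.** **1. What the two screening texts let through**

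| Person at screening | Exclusion 8 read as custom only | Exclusion 8 read as all insoles | Telephone script |
|---|---|---|---|
| Wears a custom orthotic now | excluded | excluded | screened out |
| Stopped a custom orthotic within 30 days | passes | passes | screened out |
| Wears a non-custom support now | passes | excluded | passes |
| Stopped a non-custom support yesterday | passes | passes | passes |

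The two texts disagree in at least one row under either reading of exclusion 8. A very recent user of a non-custom support passes everything. A current user passes everything on the custom-only reading.

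**2. The plan's own figure**

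Section 4 gives 50 subjects with no power, effect size, standard deviation or dropout rate, so it cannot be reproduced. For orientation, a paired t-test with n = 50 and two-sided alpha 0.05 (Section 9 gives 0.05 but no sidedness) has 80% power for a standardised change of about 0.40.

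**3. Illustration of the size**

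The documents supply none of these inputs, so all are assumptions:
- f = share of subjects already using a non-custom support
- r = fraction of the full change that those users still show
- true change in non-users = 20 mm on a pain VAS (Section 6 does not single out one questionnaire as primary)

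Pooled change = 20 × [1 − f × (1 − r)].

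- r = 0: 20 × 0.90 = 18; 20 × 0.80 = 16; 20 × 0.70 = 14 mm
- r = 0.5: 20 × 0.95 = 19; 20 × 0.90 = 18; 20 × 0.85 = 17 mm

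The same factor applied to an assumed standardised change of 0.50, with the spread of the changes left unaltered, gives these powers from the noncentral t distribution (n = 50, two-sided 0.05):

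| f | Users among 50 | r = 0: change | r = 0: d, power | r = 0.5: change | r = 0.5: d, power |
|---|---|---|---|---|---|
| 0% | 0 | 20 mm | 0.50, 93% | 20 mm | 0.50, 93% |
| 10% | 5 | 18 mm | 0.45, 88% | 19 mm | 0.475, 91% |
| 20% | 10 | 16 mm | 0.40, 79% | 18 mm | 0.45, 88% |
| 30% | 15 | 14 mm | 0.35, 68% | 17 mm | 0.425, 84% |

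If r is above 1, the factor exceeds 1 and the pooled change is too large. That could happen if users join because their present device is failing them.

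**The case against.** **Exclusion 8 may already cover all insoles.** The wording can be parsed as custom shoes, or insoles of any sort. A reader might infer that the script settles the custom-only reading. It does not. Section 5 presents the script as a first-pass screen, and formal eligibility is decided at Visit 1 against the criteria. The script also departs from those criteria elsewhere: it asks about foot surgery and neuropathy, which are not listed exclusions; it uses a 300 lb limit in place of BMI; and it omits braces, ulcers, walking aids, recent CT and pregnancy. It supports the custom-only reading without proving it. What remains is a criterion with two readings and no look-back under either.

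**The endpoint is change from baseline, not support against no support.** That is true of the Section 6 definition. Section 3 also attributes these conditions partly to inadequate or badly fitted supports, so a symptomatic wearer of a poor insole could be seen as part of the target population. This carries some weight, but it sits badly with a baseline labelled pre-treatment and with the Section 9 contrast.

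**No further change in users is a worst case.** This stands. Inclusions 3 and 4 require a symptomatic condition and at least 30 days of foot pain, so every user who enters has room to improve. The r = 0.5 columns are there for that reason.

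**Store visitors may be first-time buyers.** This also stands. Recruiting in the sponsor's store makes prior use plausible, but the documents do not show how common it is.

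**Conclusion.** The concern holds as a gap in eligibility wording with a consequence for the symptom baseline. On the natural reading of exclusion 8, current users of non-custom supports can be enrolled. On the other reading, exclusion 8 and the script conflict, and people who have only just stopped can still enter.

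The effect is confined to current or recent users, whose number is unknown. With assumed shares of 10% to 30%, a true 20 mm change would be reported as 14 to 18 mm if users show no further change, or 17 to 19 mm if they show half. Dilution is the probable direction, but the opposite is possible.

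A reader might infer that the primary result as a whole is invalid or certain to be understated. The documents do not support that: for subjects without a prior support the baseline is unsupported as intended, and neither the share of users nor their response is given. The change is cheap and should be made, but the gap does not by itself undermine the study.

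**What to change.** **Wording.** Replace exclusion 8 with: *Currently wearing, or having worn in the last 30 days, any arch support or insole, custom or non-custom, other than the liner supplied with the shoe.* Change the telephone question to match. The 30-day period is the one the protocol already uses for braces and in the script. It is adopted here for consistency, since the documents give no separate basis for insoles.

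**Subjects already enrolled.** Keep them in the primary analysis; removing them under a rule adopted after entry would be a post-hoc exclusion. Flag prior support use from the Visit 1 footwear assessment, after checking that it recorded insoles as well as shoes. Before the outcome data are analysed, specify a sensitivity analysis of the primary endpoint that leaves out the flagged subjects, to be reported beside the full-sample result.

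**Cost.** A protocol and script amendment. Some callers become ineligible, so recruitment may be slower; by how much depends on how common prior use is, which is not known.
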